9.5.1.4 Hospitalization

Time to first hospitalization and the rate of hospitalization due to serious respiratory-related AEs will be analyzed using the same models as specified for the pulmonary exacerbation.

9.5.1.6 Patient reported outcomes

Quality of Life Questionnaire-Bronchiectasis (QoL- B)

QOL-B Respiratory Symptom domain contains 9 items, and each of the 37 items is scored from 1 to 4, and the overall score is standardised on a 0-100 point scale, with higher scores representing fewer symptoms or better functioning.

Items in the questionnaire are expressed either “negatively” or “positively,” therefore a number of items must be recorded before the scores for each of the domains are calculated. The score is calculated by adding the score obtained for each item of a domain (scale), after any necessary recoding. Scoring for each domain can be computed only if at least half the items have been completed. If not, then the domain should not be scored and should be considered missing for that particular person who filled out the questionnaire.

The minimum or maximum score always corresponds to the highest QOL and the minimum score always corresponds to the lowest QOL.

Change from baseline in QOL-B Respiratory Symptom Score (RSS) will be analyzed using a linear repeated measure model. The model will contain treatment, baseline macrolide use, visit (visits 102 to 202), and treatment-by-visit interaction as fixed effects with baseline QOL-B RSS, baseline-by-visit interaction as covariates. The within-patient correlation will be modeled using the unstructured covariance matrix in the mixed model. If the model does not converge, then the compound symmetry covariance structure will be used Restricted maximum likelihood method will be used.

9.5.2 Safety variables

All safety analyses will be performed using the safety population, and will be presented by treatment groups. Baseline for safety analyses is defined as the last measurement prior to the first dose of study medication in the study.

Appropriate summary statistics will be provided for laboratory test results, audiology, bronchial hyperreactivity and vital signs.

AEs will be deemed treatment-emergent if the onset date is on or after the date of first study drug and until study completion. Treatment emergent AEs will be summarized by MedDRA primary SOC and preferred term for each cycle and overall. The actual MedDRA version in effect at the time of the clinical study report will be used for coding AEs.

Audiology testing will be performed at selected centers and in patients with hearing events. Audiology function data will be analyzed via summary statistics by treatment and visit.

Clinical laboratory parameters will be summarized using means and mean changes from baseline to each post-baseline visit by treatment group. Shift-from-baseline summaries (shift tables) will be presented for the last available measurement (Termination Visit).

Vital sign parameters will be summarized using means and mean changes from baseline by treatment group and visit.

Analysis of post-inhalation events will be conducted for the two types of events (post-inhalation clinical events/post-inhalation adverse events). The number of patients with post-inhalation events will be summarized by treatment. In addition, the number of these events and the event rate adjusted for exposure will be displayed by treatment.

Post-inhalation events occurring at a site visit within 5 minutes (yes/no), post-inhalation events that are ongoing at completion of the site visit (yes/no) and for which an action taken to reduce the event (yes/no), the time-point of an event and the time of onset (≤ 30 sec, >30 sec-1min, >1 -2min, >2 -5min, >5 min) will be summarized with the number and percentage overall and for each cycle. Descriptive statistics including mean, standard deviation, minimum, median and maximum will be provided for the duration of the event in seconds.

[figure not shown]
Bronchial hyperreactivity will be measured as the acute relative change from pre-dose to 30 ± 15 minutes post-dose in FEV₁% predicted at Visits 101, 102, 103, 104, 105 and 106. A change of 20% or more is considered a clinically significant indicative of bronchospasm/bronchial hyperreactivity. This change will be summarized with the number and percentage of patients who experienced no change, a decrease/increase of >0 - $<10\%$, a decrease/increase of 10 - $<20\%$ or a decrease/increase $\geq 20\%$. Both analyses will also be done for the patients who did the post-dose spirometry test in a 60 minutes time window.

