3.1 Study design

[figure not shown]
This is a blinded, randomized, dose and regimen finding trial utilizing a 3 treatment cohort design where active TIP doses or placebo in addition to the local standard care within each cohort are delivered once or twice daily. Approximately 180 eligible patients will be randomized to one out of the 3 cohorts in a ratio of 1:1:1. The patients within each cohort will be randomized to blinded TIP or placebo with the following randomization scheme: TIP: TIP/placebo cyclical: placebo, in a 2:2:1 ratio. In total, the study has nine treatment arms distributed among the 3 cohorts (see [Section 5.1](#)). Total duration of the study is expected to be up to 196 days with a total of 9 visits, consisting of up to 28 days for the screening epoch; after randomization a 112-day treatment epoch with 6 clinic visits, followed by a 56-day follow-up epoch with 2 clinic visits. Patients will be assessed for safety, tolerability and efficacy (see Assessment Schedule [Table 6-1](#)).

At an initial screening visit (Visit 1), informed consent will be obtained before any study related assessment or procedures are performed, inclusion/exclusion criteria will be assessed and current medications reviewed. All patients signing informed consent must be registered in the Interactive Response Technology (IRT). The patients will commence a flexible 7-28 day screening epoch where all screening assessments will be performed and the presence of pulmonary bacterial colonization with *P. aeruginosa* based on sputum culture will be done. Patients who are otherwise eligible may be re-tested for *P. aeruginosa* in the sputum and/or laboratory evaluations during the screening epoch. Any patient can be re-screened once until enrollment has completed. Patients who had an exacerbation during the screening phase can be re-screened twice until recruitment has been completed. The *P. aeruginosa* bacterial load estimation will be done by quantitative identification using standard culture methods ([Patel et al 2002](#)). [REDACTED]. At

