5.6.2 Discontinuation of Study Treatment

Discontinuation of study treatment for a patient occurs when study drug is stopped earlier than the protocol planned duration, and can be initiated by either the patient or the investigator.

The investigator must discontinue study treatment for a given patient if, on balance, he/she believes that continuation would negatively impact the risk/benefit of trial participation.

Study treatment **must** be discontinued under the following circumstances:

- Patient wish
- Non-compliance of the patient with study procedures or investigator instructions, as per the investigator's judgment

- Emergence of AEs when worsened from baseline (Visit 2) or any newly occurring development of AEs with regards to the following:
 - If a patient is found to have a 20-dB or greater decrease in auditory acuity at one or more frequencies in 1 or both ears due to sensorineural deficit, the patient will be withdrawn from treatment and monitored until auditory acuity values return to the most recent pre-dose value (either at screening or baseline) or until study closure, whichever occurs first, i.e. the patient must be withdrawn from study treatment but should continue in the study. In case no pre-dose value is available for comparison, discontinuation of the study treatment and withdrawal of the patient from the study should be based on the investigator's best medical judgment.
- Any of the following laboratory abnormalities when worsened from baseline (Visit 101) or are a newly occurring AE:
 - Proteinuria $\geq 3+$, as confirmed according to Section 14, Appendix 2 Specific Renal Alert Criteria and Actions
 - Serum creatinine increase $\geq 50\%$ compared to baseline, as confirmed according to Section 14, Appendix 2 Specific Renal Alert Criteria and Actions
 - Estimated glomerular filtration rate (GFR) of ≤ 50 mL/min/1.73m²
- Pregnancy (see [Section 6.5.8](#) and [Section 7.6](#))
- Use of any of the prohibited medications detailed in [Table 5-1](#) and [Section 5.5.8](#).
- Any situation in which study participation might result in a safety risk to the patient.

Any renal finding needs to be followed up according to [Section 14 Appendix 2](#) Specific Renal Alert Criteria and Actions, which lists additional laboratory abnormalities that may require study treatment discontinuation based on clinical judgement. Confirmed renal events need to be followed up and documented according to [Section 14 Appendix 2](#).

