7.1 Adverse events

An adverse event (AE) is any untoward medical occurrence (e.g., any unfavorable and unintended sign [including abnormal laboratory findings], symptom or disease) in a subject or clinical investigation subject *after providing written informed consent* for participation in the study until the end of study visit. Therefore, an AE may or may not be temporally or causally associated with the use of a medicinal (investigational) product.

In addition, all reports of intentional misuse and abuse of the product are also considered an adverse event irrespective if a clinical event has occurred.

The occurrence of adverse events must be sought by non-directive questioning of the patient at each visit during the study. Adverse events also may be detected when they are volunteered by the patient during or between visits or through physical examination findings, laboratory test findings, or other assessments.

Abnormal laboratory values or test results constitute adverse events only if they fulfill at least one of the following criteria:

- they induce clinical signs or symptoms,
- they are considered clinically significant,
- they require therapy.

Clinically significant abnormal laboratory values or test results must be identified through a review of values outside of normal ranges/clinically notable ranges, significant changes from baseline or the previous visit, or values which are considered to be non-typical in patient with underlying disease. Investigators have the responsibility for managing the safety of individual patient and identifying adverse events. Alert ranges for laboratory and other test abnormalities are included in [Appendix 1](#).

Adverse events must be recorded in the Adverse Events CRF under the signs, symptoms or diagnosis associated with them, accompanied by the following information:

- the severity grade
 - mild: usually transient in nature and generally not interfering with normal activities
 - moderate: sufficiently discomforting to interfere with normal activities
 - severe: prevents normal activities
- its relationship to the study treatment (no/yes)
- its duration (start and end dates) or if the event is ongoing an outcome of not recovered/not resolved must be reported.

- whether it constitutes a serious adverse event (SAE – See [Section 7.2](#) for definition of SAE)
- action taken regarding study treatment

All adverse events must be treated appropriately. Treatment may include one or more of the following:

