- no action taken (e.g. further observation only)
- study treatment dosage adjusted/temporarily interrupted
- study treatment permanently discontinued due to this adverse event
- concomitant medication given
- non-drug therapy given
- patient hospitalized/patient's hospitalization prolonged (see [Section 7.2](#) for definition of SAE)
- its outcome (not recovered/not resolved; recovered/resolved; recovering/resolving, recovered/resolved with sequelae; fatal; or unknown)

Once an adverse event is detected, it must be followed until its resolution or until it is judged to be permanent, and assessment must be made at each visit (or more frequently, if necessary) of any changes in severity, the suspected relationship to the study drug, the interventions required to treat it, and the outcome.

Information about common side effects already known about the investigational drug can be found in the Investigator Brochure (IB). This information will be included in the patient informed consent and should be discussed with the patient during the study as needed. Any new information regarding the safety profile of the medicinal product that is identified between IB updates will be communicated as appropriate, for example, via an Investigator Notification or an Aggregate Safety Finding. New information might require an update to the informed consent and has then to be discussed with the patient.

The investigator must also instruct each patient to report any new adverse event (beyond the protocol observation period) that the patient, or the patient's personal physician, believes might reasonably be related to study treatment. This information must be recorded in the investigator's source documents; however, if the AE meets the criteria of an SAE, it must be reported to Novartis.

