7.2.2 SAE reporting

To ensure patient safety, every SAE, regardless of causality, occurring after the patient has provided informed consent and until 30 days after the last study visit must be reported to Novartis within 24 hours of learning of its occurrence. Any SAEs experienced after the 30 day period after the last study visit should only be reported to Novartis if the investigator suspects a causal relationship to study treatment.

All follow-up information for the SAE including information on complications, progression of the initial SAE and recurrent episodes must be reported as follow-up to the original episode within 24 hours of the investigator receiving the follow-up information. An SAE occurring at a different time interval or otherwise considered completely unrelated to a previously reported one must be reported separately as a new event.

Information about all SAEs (*either initial or follow-up information*) is collected and recorded on the paper Serious Adverse Event Report Form. The investigator must assess the relationship to *each specific component of study treatment*, complete the SAE Report Form in

English, and send the completed, signed form by fax within 24 hours after awareness of the SAE to the local Novartis Drug Safety and Epidemiology Department. The telephone and fax number of the contact persons in the local department of Drug Safety and Epidemiology, specific to the site, are listed in the investigator folder provided to each site. The original copy of the SAE Report Form and the fax confirmation sheet must be kept with the case report form documentation at the study site. Follow-up information should be provided using a new paper SAE Report Form stating that this is a follow-up to a previously reported SAE.

Follow-up information provided must describe whether the event has resolved or continues, if and how it was treated, whether the treatment code was broken or not and whether the patient continued or withdrew from study participation. Each re-occurrence, complication, or progression of the original event must be reported as a follow-up to that event regardless of when it occurs.

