2.7.1 Adverse events (AEs)

An AE will be classified as a treatment emergent AE (TEAE) if it starts on or after the date of the first dose of study drug until study completion.

TEAEs will be summarized by System Organ Class (SOC) and Preferred Term (PT) using the latest Medical Dictionary for Drug Regulatory Affairs (MedDRA) available at the time of database lock.

The number and percentage of patients experiencing TEAEs, SAEs, AEs suspected to be related to study drug, AEs leading to study drug discontinuation and AEs leading to death will be summarized by treatment arm and overall.

The number and percentage of patients experiencing TEAEs will be summarized by treatment arm by SOC and PT, and by SOC, PT and maximum severity. In addition, the number and percentage of patients experiencing AEs suspected to be related to study drug will be summarized by treatment arm by SOC and PT.

For the legal requirements of ClinicalTrials.gov and EudraCT, two required tables on TEAEs which are not serious adverse events with an incidence greater than 5% and on treatment emergent SAEs and SAEs suspected to be related to study treatment will be provided by SOC and PT using the SAF.

If for the same patient, several consecutive AEs (irrespective of study treatment causality, seriousness and severity) occurred with the same SOC and PT:

- a single occurrence will be counted if there is ≤ 1 day gap between the end date of the preceding AE and the start date of the consecutive AE
- more than one occurrence will be counted if there is > 1 day gap between the end date of the preceding AE and the start date of the consecutive AE

For occurrence, the presence of at least one SAE / SAE suspected to be related to study treatment / non SAE has to be checked in a block e.g., among AEs in a ≤ 1 day gap block, if at least one SAE is occurring, then one occurrence is calculated for that SAE.

The number of deaths resulting from SAEs suspected to be related to study treatment and SAEs irrespective of study treatment relationship will be provided by SOC and PT.

AEs of special interest (AESIs):

The number and percentage of patients with AEs regarding ototoxicity and/or hemoptysis and renal events will be summarized. Specific AE terms will be collected on the AESI electronic case report forms (eCRFs). These data include symptoms, medical history and relevant local assessment.

In addition, post-inhalational adverse events will be summarized as instructed 2.7.4.3.

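### Treatment-emergent status rests on AE start date alone, so an event that begins in screening and worsens on study drug can be left out of the TEAE tables unless the site opens a new record

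*Protocol*

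**What the plan says.** **Definition.** Protocol 9.5.2: "AEs will be deemed treatment-emergent if the onset date is on or after the date of first study drug and until study completion". SAP 2.7.1 agrees: "An AE will be classified as a treatment emergent AE (TEAE) if it starts on or after the date of the first dose"; its window likewise closes when the patient completes the study. Neither mentions a pre-dose event that changes after dosing.

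**Collection.** Protocol 7.1 counts AEs from informed consent, and Table 6-1 has them entered in the database at Visits 1 and 2. Protocol 3.1 sets the gap before dosing: "The patients will commence a flexible 7-28 day screening epoch".

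**Changes after onset.** Under Protocol 7.1 a detected AE is followed to resolution, and "assessment must be made at each visit (or more frequently, if necessary) of any changes in severity". Protocol 7.2.2 says of SAEs: "Each re-occurrence, complication, or progression of the original event must be reported as a follow-up to that event regardless of when it occurs". The same section also asks for a separate report when an SAE falls in a different time interval or is unrelated to the earlier one.

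**Use.** Safety and tolerability by dose and regimen is a primary objective (Protocol 2.1, SAP 1.2.1). The tolerability endpoint is the rate and severity of local AEs, for which SAP Table 1-1 gives cough, bronchospasm, dysgeusia and dry mouth as examples. In SAP 2.7.1 the SOC/PT tables, the maximum-severity table and the registry tables are restricted to treatment-emergent events.

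**The concern.** Patients with bronchiectasis have respiratory symptoms that vary from week to week, and a cough or breathlessness that starts in screening may be aggravated by inhaled powder. That aggravation is what a tolerability comparison across doses needs to count. If the event stays on its existing record, its start date precedes first dose and the definition drops it.

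Other parts of the protocol do treat worsening as something that emerges. The discontinuation criteria in Protocol 5.6.2 refer to "Emergence of AEs when worsened from baseline (Visit 2) or any newly occurring development of AEs", and the SAE definition in 7.2.1 covers worsening of a pre-existing condition. The analysis rule has no counterpart to either.

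At stake are the TEAE incidence and the severity distribution by arm. The rule is the same in every arm. But if a dose does aggravate symptoms, more events would be dropped where aggravation is greater, which would draw the arms together.

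**Working it through.** The plan states no figure on this point, so there is none to reproduce. The check is of the text, followed by the weight of one patient.

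**Step 1. Which events the rule loses.**

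| Situation | Start date used | TEAE? |
|---|---|---|
| Condition present before consent (medical history, Protocol 6.2 and 6.5.1) worsens after dosing | Post-dose; no earlier AE record exists | Yes |
| AE starts in screening, worsens after dosing, site opens a new record | Post-dose | Yes |
| AE starts in screening, worsens or becomes serious after dosing, same record kept | Pre-dose | **No** |
| Pulmonary exacerbation in screening (Protocol 6.4.4) | Patient is screen failed | Not applicable |
| AE starts on Day 1 before the first inhalation | Same calendar date as first dose | Yes |
| Partial start date in the month of first dose, AE not known to have ended before treatment (SAP 5.1.2) | Imputed to after first dose | Yes |

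Only the third row is lost. Whether an event falls in the second or the third row depends on how the site records it. Protocol 7.1 asks for the change in severity to be assessed, but does not say that it starts a new record. It lists a severity grade and start and end dates for each AE, and no date of severity change.

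**Step 2. Which summaries in SAP 2.7.1 are affected.**

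- Restricted to treatment-emergent events, so the event is missing: SOC/PT, SOC/PT by maximum severity, and the registry tables (non-serious TEAEs above 5%, treatment-emergent SAEs).
- Not labelled treatment-emergent, so the event may be counted: SAEs, AEs suspected to be related, AEs leading to discontinuation, AEs leading to death, and AEs of special interest.

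The maximum-severity table is the only severity table that SAP 2.7.1 specifies for AEs.

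**Step 3. Weight of one patient.** Inputs: 180 planned and 107 randomized (SAP 1); cohorts 1:1:1; 2:2:1 within cohort (Protocol 3.1). It is assumed that the planned ratios held at 107.

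- Active arm: n = N/3 × 2/5. Planned 180/3 × 2/5 = 24; actual 107/3 × 2/5 = 14.3.
- Placebo arm within a cohort: n = N/3 × 1/5. Planned 12; actual 7.1.
- One patient moves incidence by 100/n. Planned: 100/24 = 4.2 points (active) and 100/12 = 8.3 points (placebo). Actual: 100/14.27 = 7.0 and 100/7.13 = 14.0 points.
- SAP 2.7 also shows pooled placebo: 3 × 7.13 = 21.4 patients, so 100/21.4 = 4.7 points.

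**Step 4. Number of patients affected.** The documents give no rate. For illustration only, suppose 10% to 15% of patients enter dosing with an ongoing screening AE and 10% to 30% of those worsen. Then 107 × 0.10 × 0.10 = 1.1 to 107 × 0.15 × 0.30 = 4.8 patients would be affected over the whole trial. These inputs have no source in the documents, and zero cannot be excluded.

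**The case against.** The strongest reply is that the documents never say a worsened event keeps its old start date.

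- Protocol 7.1 asks only for changes to be assessed.
- Protocol 7.2.2 governs the SAE form sent to drug safety, not the onset date on the AE page, and it also provides for separate reporting.
- The SAP 2.7.1 counting rule for consecutive AEs with the same SOC and PT presupposes that one continuing event may be held as several records that differ in severity or seriousness.
- Protocol 7.2.1 lets worsening be an event in its own right.

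This stands as far as it goes. It rules out the reading, which a reader might infer from the definition alone, that such an event can never be treatment-emergent. It does not show that a new record will be opened, because no section instructs it.

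The exposed group is also narrow. Acute conditions are excluded, clinically stable pulmonary status is required, screening exacerbations lead to screen failure, and conditions from before consent go to medical history. That is correct, and it is why the effect is probably small. Isolated symptoms that start between consent and Day 1 remain.

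Tolerability is also measured outside the TEAE rule, through post-inhalation events and acute FEV1 change at dosing visits, and all AE data are listed. The Day 1 and partial-date conventions add TEAEs. These points are fair, but they concern other measures or other events. None puts a fully dated screening AE that worsens on a single record back into the SOC/PT or severity tables.

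Finally, safety is descriptive, and SAP 1 already calls inferential results exploratory after early closure. That limits the consequence. It does not make the count right.

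**Conclusion.** The point holds in limited form. Both documents classify by start date only, and recording of a worsening is left to site habit. A screening-onset AE that worsens or becomes serious on study drug is therefore left out of the TEAE tables by SOC/PT and maximum severity and out of the treatment-emergent SAE table, unless the site opens a new record. The unlabelled summaries may still count it.

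A reader might go further and conclude that the primary safety endpoint is understated. The documents do not support that. They give no rate of such events, SAP Table 1-1 words the safety endpoint as AEs and SAEs without a treatment-emergent restriction, and two date conventions push TEAE counts upward. The supportable statement is that safety and tolerability may be understated, by an unknown and probably small amount.

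The only size that follows from the documents is the weight of one patient at 107 randomized: about 7 points in an active arm and 14 in a cohort placebo arm, if the planned allocation held. With safety presented by cohort and treatment arm, a single such patient is visible.

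**What to change.** 1. In Protocol 9.5.2 and SAP 2.7.1, define a TEAE as an AE that starts on or after first dose, or one present before first dose that increases in severity or becomes serious on or after first dose. Count it at its post-dose severity.
2. In Protocol 7.1, state that such a worsening is entered as a new AE record dated at the worsening. The clause in item 1 works only if that date or record exists.
3. In SAP 2.7.1, set the treatment-emergent flag on each record before consecutive records are merged, so that a merged block does not take on the pre-dose date.
4. In SAP 2.7.1, state whether the SAE, related, discontinuation, death and special-interest summaries are limited to treatment-emergent events. If they are not, they also count events confined to screening.
5. For data already collected, derive the flag from existing severity, seriousness and SAE follow-up information where available.

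The cost is one sentence in each definition, a derivation flag and a CRF completion note. The downsides are a few more TEAEs in each arm and limited recovery for records already closed. Recruitment had stopped when the SAP was written, so the site instruction comes late for much of the data.
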